For participants who die without objective disease progression, DOR will be censored on the date of death, regardless of cause. For a participant who discontinues early from Part B of the study with no objective disease progression, DOR will be censored on the date of their last available (scheduled or unscheduled) tumor assessment at which a lack of objective disease progression was determined. Participants who discontinue study treatment but who do not have documented objective disease progression (i.e. according to the RECIST guidelines), DOR will be censored at the date of their last available (scheduled or unscheduled) tumor assessment at which a lack of objective disease progression was determined. Such participants might include those that are ongoing in Part B at the time of any defined data cut-off. Likewise, participants who have not discontinued early and do not have disease progression after a confirmed or unconfirmed response, DOR will be censored at the date of their last available (scheduled or unscheduled) tumor assessment.

In the sensitivity analyses of duration of confirmed response and duration of unconfirmed response, the same censoring rules will apply except that the date of last contact will be used for the censoring of participants who discontinue early from Part B or complete Part B without objective disease progression, clinical disease progression or death.

Date of last contact will be the latest of the dates of premature study termination and of last contact recorded on Study Termination eCRF page, the date of death, the date of last dose of study treatment, the dates of all visits, AE start and end dates (with partial dates imputed as earliest possible) and the date of contact recorded on the Survival Safety Follow-up and Survival Final Follow-up eCRF forms.

Further details on the rules to apply in the derivation of DOR are included in the Derivation of Efficacy Endpoints document which has been developed to support this SAP.

Progression-free survival (PFS) will be calculated as the time in days from the first dose of UCB6114 to the date of the first documented objective disease progression (i.e. according to the RECIST guidelines), or death due to any cause, whichever occurs first. The following calculation will be performed:

$$PFS = \left(\text{Date of Objective Progressive Disease} - \text{Date of First Dose of UCB6114} \right) + 1$$

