Participants who die due to any cause without a documented objective disease progression will be considered to have progressed on the date of their death. Participants who do not have any post-Baseline tumor assessments will be censored on the date of their first dose of UCB6114. Participants who discontinue early from Part B or discontinue study treatment without

documented objective disease progression or death, will be censored on the date of their last available (scheduled or unscheduled) tumor assessment at which a lack of objective disease progression was determined. Participants who start anti-cancer therapy during Part B without a prior documented objective disease progression will be censored on the date of their last available (scheduled or unscheduled) tumor assessment prior to the initiation of the subsequent anti-cancer therapy. If anti-cancer therapy starts on the same date as the participant's tumor assessment and determination of objective disease progression, or the participant's death (due to any cause), then the participant will not be censored and the participant will be included as having an uncensored event on this date. This censoring rule will also be applied to participants who are ongoing at any data cut-off for an analysis of Part B data who have no documented objective disease progression. The use of anti-cancer therapy during Part B will be identified via ongoing medical review of the concomitant medications together with the start dates of further anti-cancer therapy information recorded on the survival follow-up pages of the eCRF.

As a sensitivity analysis, PFS will also be calculated as the time in days from the first dose of UCB6114 to the date of the first documented objective disease progression (per RECIST 1.1), the date of clinical disease progression, as determined by the investigator, or the date of death due to any cause, whichever occurs first. Last contact date will be used for the censoring of participants still alive with no reported disease progression (objective or clinical). The same rules described above for the censoring of participants who start anti-cancer therapy will be applied in this sensitivity analysis.

Further details on the rules to apply in the derivation of PFS are included in the Derivation of Efficacy Endpoints document which has been developed to support this SAP.

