The investigator's overall tumor response assessment will be summarized using frequency counts and percentages over time (tumor assessment). Post-Baseline tumor assessments are scheduled to be performed per protocol every 8 weeks from Day 1 (± 7 days). For the purpose of this summary, the first post-Baseline tumor assessment (scheduled or unscheduled) will be assigned to ‘Tumor Assessment 1’ using the protocol-defined window of Day 50 to 64 (Day 57 ± 7 days) relative to Day 1 (first dose of UCB6114). For all subsequent post-Baseline tumor assessments (scheduled or unscheduled, but excluding tumor assessments performed at the SFU visit), these will be assigned to ‘Tumor Assessment 2’, ‘Tumor Assessment 3’ etc. using the protocol-defined window of Day 50-64 relative to the previous post-Baseline tumor assessment. If a post-Baseline tumor assessment is missed, then the scheduled day of the missed assessment will be used to window the next tumor assessment. In cases where a scheduled and unscheduled tumor assessment occurs in the same window, the investigator's overall tumor response at both assessments will be considered. If the overall tumor response is NE at one of the assessments, then the overall tumor response from the other assessment will be included in the summary table. If the overall tumor response is not NE at both assessments, then the tumor assessment that is closest to the target day of the tumor assessment will be included in the summary table. In the event that the two tumor assessments are equidistant from the target day of the tumor assessment and neither have an overall tumor response of NE, then the worst case overall tumor response will be included in the summary table. Otherwise, if the post-Baseline tumor assessment falls outside of the protocol-defined window, it will be classified as an unscheduled assessment and not included in the summary of overall tumor response.

Bar charts will also be produced for overall tumor response rate by treatment group for each visit. In addition, waterfall plots of participants' percentage change from Baseline in the sum of dimensions for all target lesions will be presented by treatment group and visit. The individual participants' bars will be colored by overall tumor response at the visit.

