Participants who die due to any cause without a documented objective disease progression will be considered to have progressed on the date of their death. Participants who do not have any post-Baseline tumor assessments will be censored on the date of their first dose of study treatment. Participants who discontinue early from Part C or discontinue study treatment without

documented objective disease progression or death, will be censored on the date of their last available (scheduled or unscheduled) tumor assessment at which a lack of objective disease progression was determined. Participants who start anti-cancer therapy during Part C without a prior documented objective disease progression will be censored on the date of their last available (scheduled or unscheduled) tumor assessment prior to the initiation of the subsequent anti-cancer therapy. If anti-cancer therapy starts on the same date as the participant's tumor assessment and determination of objective disease progression, or the participant's death (due to any cause), then the participant will not be censored and the participant will be included as having an uncensored event on this date. This censoring rule will also be applied to participants who are ongoing at any data cut-off for an analysis of Part C data who have no documented objective disease progression. The use of anti-cancer therapy during Part C will be identified via ongoing medical review of the concomitant medications together with the start dates of further anti-cancer therapy information recorded on the survival follow-up pages of the eCRF.

As a sensitivity analysis, PFS will also be calculated as the time in days from the first dose of study treatment to the date of the first documented objective disease progression (per RECIST 1.1), the date of clinical disease progression, as determined by the investigator, or the date of death due to any cause, whichever occurs first. Last contact date will be used for the censoring of participants still alive with no reported disease progression (objective or clinical). The same rules described above for the censoring of participants who start anti-cancer therapy will be applied in this sensitivity analysis.

Further details on the rules to apply in the derivation of PFS are included in the Derivation of Efficacy Endpoints document which has been developed to support this SAP.

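### Two censoring rules in Section 10.1.1 (PFS at new anti-cancer therapy, DOR for responders not discontinued) omit the no-progression condition of the adjacent rules, so read literally a not-evaluable scan can set the censoring date

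*SAP*

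**What the plan says.** All the rules are in SAP Section 10.1.1, and the Part B and Part C plans share the pattern.

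- **PFS, discontinuation.** Participants who leave the study early or stop study treatment without progression or death are censored at the "last available (scheduled or unscheduled) tumor assessment at which a lack of objective disease progression was determined".
- **PFS, new therapy.** Participants who start anti-cancer therapy without prior documented progression are "censored on the date of their last available (scheduled or unscheduled) tumor assessment prior to the initiation of the subsequent anti-cancer therapy". No condition is placed on what that assessment showed.
- **PFS, no scans.** Participants with no post-Baseline tumor assessment at all are censored at first dose.
- **PFS, ongoing at a cut-off.** A sentence after the new-therapy rules extends the censoring rule to ongoing participants without saying which rule is meant.
- **DOR, discontinuation.** Both rules (early study discontinuation, treatment discontinuation) carry the condition. The second adds: "Such participants might include those that are ongoing in Part B at the time of any defined data cut-off".
- **DOR, not discontinued.** For "participants who have not discontinued early and do not have disease progression after a confirmed or unconfirmed response, DOR will be censored" at the last available assessment, again with no condition.

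Section 10.1.2 treats NE as a possible result of a tumor assessment ("If the overall tumor response is NE at one of the assessments"). Section 4.3 feeds all scheduled and unscheduled assessments into DOR and PFS. For both endpoints, Section 10.1.1 refers to a separate Derivation of Efficacy Endpoints document for further rules.

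**The concern.** An NE scan does not establish that the disease has not progressed. The discontinuation rules allow for this by requiring that lack of progression was determined; the other two sentences do not. Three things follow from the text.

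1. An NE scan can become the censoring date under the two unconditioned rules.
2. A participant who stops study treatment without progression and then starts new therapy meets both PFS rules. If the last scan before the new therapy was NE, the rules give different dates and no order of precedence is stated. Two programmers could each follow the plan and obtain different PFS times.
3. A discontinuer whose only post-Baseline scans are NE has no PFS date. No scan showed lack of progression, and the first-dose rule covers only participants with no post-Baseline assessment.

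At stake are the Kaplan-Meier quartiles and the 3-, 6- and 9-month PFS and DOR rates of Section 10.1.2, reported for very small dose groups. The PFS sensitivity analysis reuses the new-therapy rules, so it inherits the first problem.

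**Working it through.** The plan states no figure to reproduce. The check compares the rules and then shows the possible effect on assumed data.

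**Step 1: rules side by side**

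| Endpoint and situation | Censoring date | Lack of progression required? |
|---|---|---|
| PFS, left study or stopped treatment | last available assessment | yes |
| PFS, new anti-cancer therapy | last available assessment before it | no |
| DOR, left study or stopped treatment | last available assessment | yes |
| DOR, not discontinued early | last available assessment | no |
| PFS, no post-Baseline assessment | first dose | not applicable |

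**Step 2: dates**

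Section 10.1.2 puts the first scan at Day 57 ± 7 days, with scans every 8 weeks, so the nominal second scan is 57 + 56 = Day 113.

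- PFS, evaluable scan Day 57, NE scan Day 113, then new therapy: Day 113 literally, Day 57 with the condition. Difference 113 − 57 = 56 days.
- DOR, first response Day 57, confirmed Day 113, NE Day 169, ongoing: literally (169 − 57) + 1 = 113 days; with the condition (113 − 57) + 1 = 57 days.

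These are nominal values. Visit windows, unscheduled scans or consecutive NE scans change the gap.

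**Step 3: direction**

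The Kaplan-Meier estimate is the product of (1 − d/n) over event times. Moving one censoring date later adds one to n at every event time after the old date and up to the new one, which raises those factors. With no event in that span, nothing changes.

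**Step 4: size in one assumed case**

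Nine participants, the maximum evaluable number per dose level in Section 2.3. The event pattern is assumed: PFS events on Days 57, 57, 57, 85, 100, 113, 169 and 169, plus one participant with an evaluable scan on Day 57, an NE scan on Day 113, then new therapy.

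- Literal rule (censored Day 113), PFS at Day 120: 6/9 × 5/6 × 4/5 × 3/4 = 33.3%.
- Conditioned rule (censored Day 57), PFS at Day 120: 6/9 × 4/5 × 3/4 × 2/3 = 26.7%.
- PFS at Day 91: 6/9 × 5/6 = 55.6% against 6/9 × 4/5 = 53.3%.

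If one of the Day 169 events is replaced by a second affected participant, PFS at Day 120 is 33.3% against 6/9 × 3/4 × 2/3 × 1/2 = 16.7%.

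**The case against.** The strongest reply is that the plan nowhere says an NE scan counts; that comes from reading a missing phrase literally. The Derivation of Efficacy Endpoints document, which is not available here, may hold an NE rule. The DOR sentence opens with *Likewise* directly after two conditioned rules, so the condition may have been meant to carry over. Both PFS rules can also be satisfied together by taking the last scan before the new therapy that showed no progression. All of this stands as a reason for caution about intent. It does not remove the difference in wording or supply a precedence.

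The DOR part is also narrow. Section 3.2.3 ends Part B at the last participant's Final Visit, 3 months after the last dose. By then participants are off treatment, and the conditioned rule for treatment discontinuers already applies to them. The unconditioned sentence matters mainly at interim cut-offs.

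A reader might infer more than the documents support:

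- *That the plan counts NE scans as progression-free follow-up.* It permits that reading but does not state it.
- *That every affected participant gains a full scan interval and stays at risk for all progressions found in that scan round.* Scans fall in ±7-day windows and unscheduled scans count, so neither is general.
- *That PFS and DOR are biased upward by a known amount.* The comparison is with the conditioned rule, not with true PFS or DOR, and the difference is zero if no event falls in the span.
- *That the censoring date depends on why a participant left.* Someone starting subsequent therapy has normally also stopped study treatment, so the two rules overlap rather than define separate groups.
- *That any participant with only NE scans lacks a PFS rule.* For one who starts new therapy, the literal rule does give a date, the last NE scan before it. The gap concerns discontinuers without new therapy.

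**Conclusion.** The inconsistency is real in both parts of the SAP. Two censoring sentences lack a condition that their neighbours carry, two PFS rules can apply to one participant without precedence, and NE-only discontinuers have no PFS date. Followed literally, the unconditioned rules can only raise the Kaplan-Meier estimate relative to the conditioned rule, or leave it unchanged.

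The size depends on how many NE scans occur last and on which events fall in the span. The 33.3% against 26.7% at Day 120 is one assumed case with one affected participant in nine, not a forecast. The conclusion also assumes that the derivation document does not already settle NE handling.

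Severity is minor. Antitumor activity is exploratory and descriptive, analysed if data allow. The primary safety endpoints and the mTPI escalation do not use these estimates. Section 2.3 lists available antitumor activity among the inputs to the recommended Phase 2 dose, but does not tie that decision to PFS or DOR rates.

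**What to change.** In Section 10.1.1 of the Part B plan:

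1. Add the SAP's own condition, "tumor assessment at which a lack of objective disease progression was determined", to the PFS new-therapy sentence and to the DOR sentence for responders who have not discontinued early. With the condition in both PFS rules, state that the scan used must also precede any new therapy; this settles precedence.
2. Say which rule the sentence on participants ongoing at a data cut-off refers to.
3. Reword the PFS first-dose rule so that it covers participants with no evaluable post-Baseline tumor assessment, keeping deaths as PFS events.
4. Check the Derivation of Efficacy Endpoints document and align it.
5. Make the same edits in the Part C plan.

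The cost is a few wording changes in each plan before database lock, with no new data. Some censoring dates would move earlier, so some PFS or DOR estimates could be slightly lower than under the literal text.

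### In the PFS sensitivity analysis clinical progression is an event, but the new-therapy censoring rule still recognises only objective progression, so a clinical progressor who starts another therapy meets both rules

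*SAP*

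**What the plan says.** All of this is in Section 10.1.1 of the Part B SAP. Section 10.1.1 of the Part C SAP repeats it with only the Part and the name of the first dose changed.

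- **Main PFS, new therapy.** "Participants who start anti-cancer therapy during Part B without a prior documented objective disease progression will be censored on the date of their last available" tumor assessment before that therapy began. An exemption follows for therapy starting on the day of objective progression or death; those participants keep their event.
- **Sensitivity PFS, event.** To objective progression it adds "the date of clinical disease progression, as determined by the investigator, or the date of death due to any cause, whichever occurs first".
- **Sensitivity PFS, default censoring.** "Last contact date will be used for the censoring of participants still alive with no reported disease progression (objective or clinical").
- **Sensitivity PFS, new therapy.** "The same rules described above for the censoring of participants who start anti-cancer therapy will be applied in this sensitivity analysis".

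Further PFS rules are deferred to a Derivation of Efficacy Endpoints document, which is not part of the SAP text.

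**The concern.** The sensitivity analysis exists to count clinical progressions that the main analysis censors. Its default censoring rule was rewritten to recognise both kinds of progression. The new-therapy rule was carried over as it stood, still triggered by the absence of objective progression alone.

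The people caught between the two rules are a realistic group. The SAP's DOR text says clinical progression is recorded as a reason for stopping study treatment. Follow-up then runs to a Final Visit about 3 months after the last dose, and start dates of further anti-cancer therapy are collected. A clinical progressor who is fit for another line could well start it in that interval.

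If the rule is programmed as written, their events disappear and the sensitivity curve moves back toward the main one. A reader could then take the closeness of the two as robustness. Two programmers could also produce different results from the same data.

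**Working it through.** The SAP states no figure on this point, so there is nothing to reproduce. The check sets the rules against a timeline and then illustrates the effect.

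**Step 1: the rules side by side (sensitivity PFS)**

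| Rule | Recognises objective progression | Recognises clinical progression |
|---|---|---|
| Event definition | yes | yes |
| Default (last-contact) censoring | yes | yes |
| New-therapy censoring | yes | no |
| Same-date exemption | yes (and death) | no |

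**Step 2: one participant**

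Inputs: the first scan is due on Day 57 ± 7 and scans follow every 8 weeks (Section 10.1.2). PFS = event date − first-dose date + 1, with first dose on Day 1. Assumed history: scan on Day 57 without progression, clinical progression on Day 75, new therapy on Day 90.

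- Event definition: 75 − 1 + 1 = 75 days, event.
- Carried-over rule: there is no objective progression before Day 90, so censored at the Day 57 scan, 57 days.
- Main analysis: also censored at 57 days.

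For this participant the literal rule reproduces the main analysis. If the new therapy started on Day 75 itself, the conflict would remain, because the exemption does not cover clinical progression.

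**Step 3: effect on a Kaplan-Meier estimate (invented data)**

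Take 9 participants, the maximum evaluable number per dose level (Section 2.3). All are scanned on Day 57 without progression. Three progress clinically on Day 75, four objectively on Day 113 (57 + 56) and two objectively on Day 169 (113 + 56).

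| Handling | PFS at 3 months (Day 91) | PFS just after Day 113 |
|---|---|---|
| All 3 clinical progressions count | 6/9 = 67% | 6/9 × 2/6 = 22% |
| 2 of 3 start new therapy, censored at Day 57 | 6/7 = 86% | 6/7 × 2/6 = 29% |
| All 3 start new therapy, censored at Day 57 | 100% | 2/6 = 33% |
| Main analysis | 100% | 2/6 = 33% |

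Every participant here has a scan before the new therapy, so the carried-over rule supplies the censoring date by itself.

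**Step 4: a range under other assumptions**

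A simulation of 4000 trials of 27 participants assumed exponential progression times with a 90-day median and scans every 56 days. All clinical progressors start new therapy before the next scan, and there is no other censoring. PFS at 3 months:

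| Share progressing clinically | Counted as events | Literal rule | Difference |
|---|---|---|---|
| 10% | 0.63 | 0.67 | about 4 points |
| 20% | 0.62 | 0.70 | about 8 points |
| 30% | 0.60 | 0.72 | about 12 points |

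These figures also assume that clinical progressors with no scan are censored on Day 1, which the sensitivity text does not clearly provide. They show the direction and a possible range, not an estimate.

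**The case against.** The best defence is that the event definition already settles the order. It takes whichever event comes first, and a clinical progression on Day 75 precedes a therapy on Day 90. The default rule in the same paragraph recognises clinical progression, so a sensible programmer would read the new-therapy rule in that light. The derivation document may also state the precedence. This stands in part: the intended reading is available, and a reader who infers that these events will certainly be removed goes further than the text. But the SAP states the new-therapy rule explicitly and applies it unchanged. The literal reading is also workable, because clinical progressors who start no new therapy would still count. An unseen supporting document does not cure that.

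Three stronger readings are not supported.

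- **Day-1 censoring.** A reader might infer that clinical progressors with no scan would all be censored at first dose. The main analysis has that rule: "Participants who do not have any post-Baseline tumor assessments will be censored on the date of their first dose of UCB6114". It is a separate sentence, and the sensitivity paragraph imports only the new-therapy rules. For these participants the text gives no clear date.
- **The same clash in DOR.** A reader might point to the carried-over rule for "Participants who discontinue study treatment but who do not have documented objective disease progression". DOR has no new-therapy rule. Its sensitivity formula names objective or clinical progression, and a tie rule covers the two falling on one day. Read literally, the discontinuation rule would leave that formula almost no use, so clinical progression plainly counts there.
- **False confirmation of the main result.** This would need most clinical progressors to start new therapy. The SAP gives no such split.

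**Conclusion.** The conflict is real and confined to PFS in the sensitivity analysis, in both Parts. It affects only participants with clinical progression followed, on the same day or later, by new anti-cancer therapy, with no earlier objective progression. Applied literally, the rule censors them at the last scan before that therapy, and sensitivity PFS is biased upward toward the main result. The size cannot be known from the SAP; every figure above rests on assumed event patterns.

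The consequence is limited. Antitumor activity is exploratory, PFS is summarised descriptively and only if the data allow, and no decision rule depends on this analysis. Even so, the sensitivity Kaplan-Meier summaries are planned outputs (Section 10.1.2), and available antitumor activity is part of the totality used to choose the recommended Phase 2 dose (Section 2.3). The wording should be settled before database lock.

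**What to change.** In the PFS sensitivity paragraph of Section 10.1.1, Parts B and C, replace the carry-over sentence with text to this effect: in this analysis, new-therapy censoring applies only to participants with neither objective nor clinical progression on or before the start date of the new therapy; clinical progression on or before that date is an event on its own date. This also covers the same-date case. Check that the Derivation of Efficacy Endpoints document agrees.

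For DOR, at most align the wording: in the sensitivity analysis, the treatment-discontinuation rule covers participants with neither objective nor clinical progression.

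The cost is a short wording change in each Part and one programming condition. No new data are needed.
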